#### 13.4.6.4. Exploratory endpoints

The analysis of the exploratory endpoints will be further detailed in the SAP.

- To evaluate the potential association of exploratory tissue and blood biomarkers with response to tesevatinib (PFS-6) and with adverse events. These include EGFRvIII mutation and gene amplification and may include circulating tumor DNA expression of these and other factors
- To evaluate the correlation between patients with EGFRvIIIpos tumor and those patients with EGFR gene amplification with respect to survival and safety
- To evaluate and compare EGFRvIIIpos expression and/or other tissue biomarkers potentially associated with response with tesevatinib, in paired primary and recurrent glioblastoma specimens from the same patient, when these are available
- To evaluate patient-reported outcomes of disease and treatment-related symptom severity and interference as measured by the MDASI-BT questionnaire

The MDASI-BT score is analyzed using a repeated measurement analysis with the MDASI-BT score as dependent variable, baseline score as covariate and cycle as fixed effect. Patient and center as included as random effects.

The data are summarized as scores and as change from baseline, as well as the categorical variables severe, moderate and mild cognitive impairment.

• To evaluate patient-reported outcomes of disease and treatment-related symptom severity and interference as measured by the MDASI-BT questionnaire in the subgroup of patients with EGFRvIIIneg and EGFR gene amplificationneg tumors as compared to those in patients with EGFRvIIIpos and EGFR gene amplificationpos tumors

Comparisons will be performed by using the mixed model and including subgroup and a subgroup-cycle interaction.

Data will be modelled with the MDASI-BT score as dependent variable and with a categorical response (binary or three categories).

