	Thirteen items ask patients to rate how severe the symptoms were when "at their worst" in the last 24 hours with regard to pain, fatigue, nausea, disturbed sleep, distress, shortness of breath, remembering things, lack of appetite, drowsy, dry mouth, sad, vomiting, and numbness or tingling. An additional six items ask patients to rate how much the symptoms have interfered with six areas of function (general activity, walking, work, mood, relations with other people, and enjoyment of life) in the last 24 hours. The MDASI-BT (see Appendix 3) contains an additional nine items that assess symptoms and concerns specific to primary brain tumor patients (difficulty understanding, difficulty speaking, difficulty concentrating, seizures, weakness, change in appearance, change in vision, change in bowel patterns, irritability), for a total of 28 items.
	Subjects completing 24 cycles of tesevatinib will no longer be required to complete patient reported outcomes and mini-mental state examinations.
Statistical methods	Analysis populations
	Adult patients with recurrent glioblastoma, meeting all inclusion criteria and no exclusion criteria, with availability of paraffin-embedded tumor samples diagnostic of glioblastoma will be enrolled.
	Two subgroups of patients are defined as having: EGFRvIII pos and EGFR amplification pos tumors.
	Primary and secondary efficacy analyses will include all patients who were included in the study. The same analysis methods for the primary and secondary analyses will be applied to both the ITT population and the EGFRvIII pos and EGFR gene amplification pos population.
	Safety analyses will include all patients who enrolled and received at least one dose of study treatment (the safety population).
	All patients who take at least one dose of tesevatinib will be evaluable for safety and efficacy assessments.
	Patients who do not complete the study, for whatever reason, will have all available data (up until the time of termination related to the reason they were terminated) included in the analysis.
	For statistical purposes, completion of the study will be defined as six months after the last patient starts study treatment.
	The plasma concentration analysis population will consist of all patients who receive at least one dose of tesevatinib, and who have at least one sample analyzed for plasma concentrations.

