# 6.3. Exploratory objectives

- To evaluate the plasma concentrations of tesevatinib in patients with and without systemic steroid treatment
- To evaluate the potential association of exploratory tissue and blood biomarkers with response to tesevatinib and with adverse events. These include EGFRvIII mutation and gene amplification and may include circulating tumor DNA
- To evaluate the correlation between patients with EGFRvIIIpos tumor and those patients with EGFR gene amplification
- To evaluate and compare EGFRvIIIpos expression and/or other tissue biomarkers potentially associated with response with tesevatinib, in paired primary and recurrent glioblastoma specimens from the same patient, when these are available

- To evaluate patient-reported outcomes of disease and treatment-related symptom severity and interference as measured by the MDASI-BT questionnaire
- To evaluate patient-reported outcomes of disease and treatment-related symptom severity and interference as measured by the MDASI-BT in the subgroup of patients with EGFRvIIIneg and EGFR gene amplificationneg tumors as compared to those in patients with EGFRvIIIpos and EGFR gene amplificationpos tumors

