## 12.1.12. Patient Reported Outcomes (MDASI-BT)

PROs of disease- and treatment-related symptom severity and symptom interference will be assessed using the MDASI-BT questionnaire.

The MDASI is a validated and reliable self-report measure that was developed to assess symptom severity and interference [Cleeland 2000; Armstrong 2006].

Thirteen items ask patients to rate how severe the symptoms were when "at their worst" in the last 24 hours with regard to pain, fatigue, nausea, disturbed sleep, distress, shortness of breath, remembering things, lack of appetite, drowsy, dry mouth, sad, vomiting, and numbness or tingling. An additional six items ask patients to rate how much the symptoms have interfered with six areas of function (general activity, walking, work, mood, relations with other people, and enjoyment of life) in the last 24 hours. The MDASI-BT (see Appendix 3) contains an additional nine items that assess symptoms and concerns specific to primary brain tumor patients (difficulty understanding, difficulty speaking, difficulty concentrating, seizures, weakness, change in appearance, change in vision, change in bowel patterns, irritability), for a total of 28 items.

All patients will complete the self-administered questionnaire pre-dose on Day 1 of Cycles 1 and 2; every 8 weeks after enrollment (i.e., coinciding with the schedule of disease assessments); and

at the End of Study Drug Treatment visit (EOS). Additionally, patients who discontinue study treatment for reasons other than disease progression will complete the questionnaire every 8 weeks during follow-up until the time of documented disease progression. The questionnaire will take patients  $\sim$ 5–10 minutes to complete. Patients must complete the questionnaire prior to any other tests or assessments and prior to any discussion of the patient's progress with their physician or any other healthcare personnel at the site.

Subjects who have completed 24 cycles of treatment without disease progression or unacceptable toxicity will not be required to complete the MDASI-BT questionnaire at subsequent bi-monthly visits.

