## 3.9 Patient-Reported Outcomes (PRO)

Patient-reported outcomes in M.D. Anderson Symptom Inventory – Brain Tumor questionnaire (MDASI-BT) will be listed for teach subject.

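### SAP Section 3.9 replaces the protocol's MDASI-BT analysis with a per-subject listing without declaring it, and the protocol adds cognitive-impairment categories that the instrument does not provide

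*Protocol*

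**What the plan says.** Protocol Section 6.3 sets two exploratory objectives for this questionnaire. The first is overall: "To evaluate patient-reported outcomes of disease and treatment-related symptom severity and interference as measured by the MDASI-BT questionnaire". The second asks for the same outcomes "as measured by the MDASI-BT in the subgroup of patients with" EGFR-negative tumors, compared with patients whose tumors are EGFR-positive.

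Section 12.1.12 describes the instrument: "The MDASI is a validated and reliable self-report measure that was developed to assess symptom severity and interference".

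Section 13.4.6.4 leaves further detail on exploratory endpoints to the SAP, but already outlines an analysis:

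- A longitudinal model: "The MDASI-BT score is analyzed using a repeated measurement analysis with the MDASI-BT score as dependent variable, baseline score as covariate", with cycle as a fixed effect and patient and center as random effects.
- Descriptive output: "The data are summarized as scores and as change from baseline, as well as the categorical variables severe, moderate and mild cognitive impairment".
- For the second objective, the same mixed model with subgroup and subgroup-by-cycle terms.
- A further model: "Data will be modelled with the MDASI-BT score as dependent variable and with a categorical response (binary or three categories").

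SAP Section 3.9 consists of one sentence, under which outcomes from the "questionnaire (MDASI-BT) will be listed for teach subject". SAP Section 3.1.2 speaks of changes from the protocol in the primary and secondary analyses only. SAP Section 2.1 does not carry over the exploratory objectives.

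The Protocol Synopsis, in the row on patient-reported outcomes, says that patients who complete 24 cycles "will no longer be required to complete patient reported outcomes and mini-mental state examinations". Table 1 schedules no such examination.

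**The concern.** There are two separate problems.

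First, the protocol attaches three grades of cognitive impairment to a scale that measures how severe symptoms are and how far they interfere with life. No item set or cut-off is given, so a programmer could not derive the grades. A table carrying that label would describe something the questionnaire does not claim to measure.

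Second, the SAP does not supply the detail that the protocol left to it. It removes the planned summaries, model and subgroup comparison, and nothing in it tells the reader that this was a decision. Patients complete the questionnaire repeatedly through treatment. With no score defined and no analysis planned, any MDASI-BT result reported later would be post hoc.

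**Working it through.** No power, alpha or sample-size figure bears on this point. The check sets the sections side by side, with a little arithmetic.

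**1. What the instrument provides.** Section 12.1.12 gives 13 core symptom items, 9 brain-tumor items and 6 interference items: 13 + 9 + 6 = 28, which agrees with the protocol's stated total. Appendix 3 divides them into two parts. Part I covers severity, items 1 to 22 (13 + 9 = 22). Part II covers interference, items 23 to 28 (6 items). Every item runs from 0 to 10. Neither part contains a cognitive-impairment grade. Four severity items concern cognition or language (7 remembering, 15 understanding, 16 speaking, 18 concentrating), but no section says that the grades come from them.

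**2. What defines the categories.** Section 13.4.6.4 gives no items and no thresholds. It also does not say how the MDASI-BT score is formed from the 28 items, although the objective names both severity and interference. The SAP adds nothing on either matter.

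**3. Each objective against each document.**

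| Exploratory objective (Section 6.3) | Protocol 13.4.6.4 | SAP 3.9 |
|---|---|---|
| Severity and interference, all patients | Scores, change from baseline, repeated-measures model | Listing only |
| EGFR-negative versus EGFR-positive | Same model plus subgroup and subgroup-by-cycle | Listing only |

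Under the SAP, 0 of 2 objectives has a summary, model or comparison.

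**4. Whether the change is declared.** SAP Section 3.1.2 covers primary and secondary analyses, and both MDASI-BT objectives are exploratory. SAP Section 4 defers only the list of tables, figures and listings to another document, which would not by itself specify a score or a model.

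**5. What data will exist.** Table 1 marks the questionnaire at Day 1 of Cycles 1, 2, 3, 5 and 7 onward, and at the end-of-treatment visit. Section 12.1.12 continues it every 8 weeks for patients who stop treatment without progression, until progression is documented. It is no longer required after 24 cycles, when disease assessments continue (Table 2b).

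**6. How large the subgroups are likely to be.** Inputs are n = 40 (Section 13.2) and the assumed proportions in Table 7.

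- EGFRvIII-positive: 40 × 0.27 = 10.8, about 11 patients.
- EGFR-amplified: 40 × 0.57 = 22.8, about 23 patients.
- If the overall 25% PFS-6 target applied to the EGFRvIII-positive group: 10.8 × 0.25 = 2.7, about 3 patients progression-free at 6 months.

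A subgroup-by-cycle model for EGFRvIII would therefore rest on very few patients in later cycles.

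**The case against.** The strongest reply is that a listing is a defensible choice. The objectives are exploratory, about 11 EGFRvIII-positive patients are expected, and perhaps 3 of them would be progression-free at 6 months. A subgroup-by-cycle mixed model on such data would be fragile. This stands as a reason to drop that model. It does not explain why the SAP has no descriptive summary, and it does not remove the need to state the decision.

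Several stronger readings are tempting, and the documents do not support them:

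- A reader might infer that the scale is to be analysed only as cognitive impairment. The same sentence keeps scores and change from baseline, and the section also specifies a mixed model on the score. The categories are an addition and by themselves defeat neither objective.
- A reader might infer that the binary or three-category model uses the cognitive-impairment grades. That sentence does not name them.
- A reader might infer that pain, nausea or bowel symptoms would be reported as cognitive impairment, or might count non-cognitive items to measure the error. Both assume an item mapping that the protocol does not give.
- A reader might conclude that neither objective can be answered. The data are collected, and the protocol outlines an analysis for both. The gap is in what the SAP plans.
- A reader might take the grades to be left over from a mini-mental state examination. The Synopsis makes this plausible, but the documents cannot show it, nor whether the Synopsis or Table 1 is the one in error.

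**Conclusion.** The point holds in two parts. The protocol adds cognitive-impairment categories that are undefined and do not match a symptom severity and interference scale. The SAP then replaces the whole protocol analysis of the MDASI-BT with a per-subject listing and does not say so, leaving both exploratory objectives with no planned summary, model or comparison. The second part matters more.

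The consequence is limited to the patient-reported results; primary, secondary and safety conclusions are unaffected. The conclusion takes SAP Section 3.9 as the full planned analysis of this questionnaire, which is how the SAP presents it. The change is worth making because it is cheap and because the protocol already outlines the analysis.

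**What to change.** Make the change in the SAP, since Section 13.4.6.4 defers the detail to it.

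1. State that the cognitive-impairment categories will not be used, or replace them with symptom-severity categories with stated cut-offs.
2. Define a severity score and an interference score along the two parts of Appendix 3, for example the means of items 1 to 22 and of items 23 to 28. The documents contain no scoring rule, so these means are a suggestion and the sponsor should confirm the rule.
3. In Section 3.9, summarise each score and its change from Cycle 1 Day 1 by visit, overall and by EGFR subgroup.
4. Run the protocol's mixed model on each score, labelled exploratory. If the subgroup model is judged too fragile, say in Section 3.1.2 that it is dropped and why, and keep the descriptive summaries.
5. Reconcile the Synopsis reference to mini-mental state examinations with Table 1.

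The first four items cost SAP wording and a few extra tables from data already collected. Any correction to protocol text for the fifth falls under the amendment procedure in Protocol Section 16, including submission to the IRB, and could wait for the next amendment.

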## 13.4.6.5. Safety Data

Safety analyses will be performed on all patients who received any quantity of study drug. AEs that are not related to treatment and that occur more than 30 days after the administration of the last dose of treatment will not be reported or analyzed.

Safety analyses will present overall results and results by subgroups.

Safety observations and measurements include AEs, safety laboratory tests, vital sign measurements, physical examinations, ECG assessments, and plasma levels.

Treatment-emergent AEs will be summarized using MedDRA® (Version 18.1 or higher) System Organ Class (SOC) and preferred term, classified from verbatim terms. The incidence and percentage of patients with at least 1 occurrence of a preferred term will be included, according to the most severe grade using the NCI-CTCAE; Version 4.03. The number of events per

preferred term will also be summarized. Causality (relationship to study treatment) will be summarized separately.

AEs, SAEs, related AEs, related SAEs,  $\geq$  Grade 3 AEs, related  $\geq$  Grade 3 AEs, and AEs leading to withdrawal, dose modification, or treatment discontinuation will be summarized by subgroup and tesevatinib overall according to SOC and preferred terms. All AEs will be in listings. Duration of AEs will be determined and included in listings, along with action taken and outcome.

Laboratory results will be classified according to NCI-CTCAE Version 4.03 and summarized. Laboratory results not corresponding to a coded term will not be graded. Incidence of laboratory abnormalities will be summarized. The worst on-study grade after the first dose of study drug will be summarized. The incidence of  $\geq$  Grade 3 laboratory abnormalities under treatment and shifts in toxicity grading from baseline to highest grade post-baseline will be displayed. Results for variables that are not coded will be presented in the listings as below, within, and above the normal limits of the local laboratory.

Vital sign measurements will be summarized at each scheduled time point using descriptive statistics. Karnofsky performance status results will be summarized by scheduled time point. Additional statistical details will be provided in a prospective statistical plan.

Digital ECG results and wave intervals measurements will be summarized and reported by patient visit and dose cohort and/or as appropriate. QTc prolongation results will be summarized separately. Covariate analyses will be employed as necessary.

# 14. DIRECT ACCESS TO SOURCE DATA/DOCUMENTS

# 14.1. Monitoring the Study

All aspects of the study will be carefully monitored by Kadmon or authorized representatives according to GCP and standard operating procedures (SOPs) for compliance with applicable government regulations.

It is understood that the responsible Kadmon study monitor (or designee) will contact and visit the investigator regularly and will be allowed on request to inspect the various records of the trial (eCRFs and other pertinent data) provided that patient confidentiality is maintained in accordance with local requirements. The principal investigator and key trial personnel must be available to assist the monitor during these visits. The investigator (or designee) must agree to cooperate with the monitor to ensure that any problems detected during the course of these monitoring visits are resolved.

All data will be entered in a validated electronic data capture system using single data entry. Standard procedures (including following data review guidelines, manual clinical review based on patient profiles, computerized validation to produce queries, and maintenance of an audit file which includes all database modifications) will be followed to ensure accurate data. Clinical personnel will review all data listings for outliers, data inconsistencies, and spelling errors.

During the course of the study, a study monitor (CRA) will make site visits to review protocol compliance, compare eCRFs against individual patient's medical records, assess drug accountability, and ensure that the study is being conducted according to pertinent regulatory requirements. In the course of the clinical study, access will be available to Kadmon or designee (e.g., CRO) to view the eCRFs after completion of the individual sections of the study.

Electronic CRF entries will be verified with source documentation. The review of medical records will be performed in a manner to ensure that patient confidentiality is maintained. Checking the eCRFs for completeness, clarity and cross checking with source documents is required to monitor the progress of the study.

The monitor will visit the sites at regular intervals throughout the study according to the monitoring plan, to verify the adherence to the protocol and the completeness, consistency, and accuracy of the data being entered on them and clarifying any data queries. The monitor should have access to laboratory test reports and other patient records needed to verify the entries on the eCRF. The completed and corrected eCRFs/CRFs for completed visits will either be collected by the monitor at the end of the study or obtained electronically for data processing. The investigator is responsible for the timely completion of eCRFs by assigned study staff. The eCRFs should be completed within seven (7) days of the patient's visit. A copy of the eCRFs will be retained by the investigator who must ensure that it is stored in a secure place with other study documents, such as the protocol, the Investigator's Brochure, and any protocol amendments.

Upon completion of the study, the monitor will make a final assessment of the conduct of the study and inventory all clinical supplies to be returned to Kadmon.

# 14.2. Audits and Inspections

The investigator should understand that source documents for this study should be made available to appropriately qualified personnel from the Kadmon Quality Assurance Unit (or designee), or to health authority inspectors after appropriate notification.

Direct access to source data is also required for inspections and audits, and will be carried out giving due consideration to data protection and medical confidentiality. Each investigator will have assured Kadmon of full access to complete source data for study participants and associated necessary support at all times.

In addition to routine monitoring procedures, audits of clinical research activities in accordance with SOPs may be performed to evaluate compliance with the protocol, the principles of GCP and any applicable regulatory requirements. A regulatory authority or IRB may also wish to conduct an inspection (during the study or even after its completion). If a regulatory authority or IRB requests an inspection, the investigator must immediately inform Kadmon that this request has been made.

Study conduct may be assessed during the course of the study by a Clinical Quality Assurance representative(s) to ensure that the study is conducted in compliance with the protocol. This designee, as well as the CRA, will be permitted to inspect the study documents (study protocol, eCRFs, investigational product accountability, original study-relevant medical records).

All patient data will be treated confidentially. Furthermore, the study protocol, each step of the data-recording procedure and the handling of the data as well as the study report may be patient to independent review by a Quality Assurance representative. Clinical site and study audits will be conducted as necessary to assure the validity of the study data.

Initial IRB approval, and all materials approved by the IRB for this study including the patient consent form and recruitment materials must be maintained by the Investigator and made available for inspection.

